4.2 Site Registration

This study is supported by the NCI Cancer Trials Support Unit (CTSU).

Each investigator or group of investigators at a clinical site must obtain IRB approval for this protocol and submit IRB approval and supporting documentation to the CTSU Regulatory Office before they can be approved to enroll patients. Assignment of site registration status in the CTSU Regulatory Support System (RSS) uses extensive data to make a determination of whether a site has fulfilled all regulatory criteria including but not limited to the following:

- An active Federal Wide Assurance (FWA) number
- An active roster affiliation with the Lead Network or a participating organization
- A valid IRB approval
- Compliance with all protocol specific requirements

In addition, the site-protocol Principal Investigator (PI) must meet the following criteria:

- Active registration status
- The IRB number of the site IRB of record listed on their Form FDA 1572

An active status on a participating roster at the registering site

Sites participating on the NCI CIRB initiative that are approved by the CIRB for this study are not required to submit IRB approval documentation to the CTSU Regulatory Office. For sites using the CIRB, IRB approval information is received from the CIRB and applied to the RSS in an automated process. Signatory Institutions must submit a Study Specific Worksheet for Local Context (SSW) to the CIRB via IRBManager to indicate their intent to open the study locally. The CIRB's approval of the SSW is then communicated to the CTSU Regulatory Office. In order for the SSW approval to be processed, the Signatory Institution must inform the CTSU which CIRB-approved institutions aligned with the Signatory Institution are participating in the study.

4.2.1 Downloading Regulatory Documents

Site registration forms may be downloaded from the 10021 protocol page located on the CTSU Web site. Permission to view and download this protocol is restricted and is based on person and site roster data housed in the CTSU RSS. To participate, Investigators and Associates must be associated with the Corresponding or Participating protocol organization in the RSS.

- Go to <https://www.ctsu.org> and log in using your CTEP-IAM username and password.

- Click on the Protocols tab in the upper left of your screen.
- Either enter the protocol # in the search field at the top of the protocol tree, or
- Click on the By Lead Organization folder to expand, then select LAO-MA036 and protocol #10021.
- Click on LPO Documents, select the Site Registration documents link, and download and complete the forms provided. (Note: For sites under the CIRB initiative, IRB data will load to RSS as described above.)

4.2.2 Requirements For 10021 Site Registration:

-
- IRB approval (For sites not participating via the NCI CIRB; local IRB documentation, an IRB-signed CTSU IRB Certification Form, Protocol of Human Subjects Assurance Identification/IRB Certification/Declaration of Exemption Form, or combination is accepted)

4.2.3 Requirements for Protocol #10021 Site Registration for Sites Participating in the Medidata Patient Cloud ePRO to collect PRO-CTCAE Items

a. Medidata Patient Cloud ePRO

This study includes the use of Medidata Patient Cloud ePRO (electronic patient-reported outcomes). After the patient is registered to the trial via OPEN, and if the patient is willing to participate in electronic data collection, the site staff will then complete a registration for the patient to the Patient Cloud ePRO through iMedidata. Note: Site staff must have already completed required eLearning for the Patient Cloud ePRO application to register a patient and information about the training is in the ePRO Appendix. The registration to the Patient Cloud ePRO will create a unique patient registration code that the site staff will provide to the patient. The patient (with assistance from the site staff) should be instructed to download the Patient Cloud ePRO app onto his/her own device (IOS, Android, phone or tablet) and use the unique patient registration code to create an account. Once the patient's account is set up, the patient will be able to complete the submission of patient reported outcomes electronically for the trial.

For sites providing a shared institutional device for use by multiple patients on site:

- The site staff should assist the patient with access and registration to the Patient Cloud ePRO app, and the patient can then complete the electronic data submission independently. Site staff may need to assist patients with logging on to the device at each visit.

b. CRA Patient Registration Instructions for ePRO

Please visit the [Medidata Learning Tool](#) for reference information on Patient Cloud ePRO for CRAs.

- i. The subject registration process starts in iMedidata. Begin by selecting the Patient Cloud ePRO Registration link for your study

- ii. The patient management app will display, select your STUDY and SITE from the drop downs and click Launch.
- iii. Now you can register your first patient. Create a subject ID and select a Country / Language from the drop down, (these are the only required data fields). The subject initials are optional, but are helpful in identifying which subject ID maps with which activation code. When finished, click Add.
- iv. The subject added and will include the date the patient was added, the subject ID, subject initials, (if included) and a unique auto-generated activation code. The activation code is unique for each patient and linked to the subject ID, it is not interchangeable. In addition, there is a status section, which indicates if the patient has registered. When the patient has registered the status will change from "invited" to "registered".

REMINDER- SITE STAFF MUST HAVE ALREADY COMPLETED THE MEDIDATA PATIENT CLOUD TRAINING IN ORDER TO REGISTER STUDY PARTICIPANTS .PLEASE VISIT THE [MEDIDATA LEARNING TOOL](https://learn.mdsol.com/patient-cloud/en/video-library-for-providers-102101952.html) FOR REFERENCE INFORMATION ON PATIENT CLOUD EPRO FOR CRAS. [HTTPS://LEARN.MDSOL.COM/PATIENT-CLOUD/EN/VIDEO-LIBRARY-FOR-PROVIDERS-102101952.HTML](https://learn.mdsol.com/patient-cloud/en/video-library-for-providers-102101952.html)

4.2.5 Checking Site Registration Status

You can verify your site registration status on the members' section of the CTSU website.

- Go to <https://www.ctsuo.org> and log in to the members' area using your CTEP-

IAM username and password

- Click on the Regulatory tab at the top of your screen
- Click on the Site Registration tab
- Enter your 5-character CTEP Institution Code and click on Go

Note: The status given only reflects compliance with IRB documentation and institutional compliance with protocol-specific requirements as outlined by the Lead Network. It does not reflect compliance with protocol requirements for individuals participating on the protocol or the enrolling investigator's status with the NCI or their affiliated networks..

4.3 Patient Registration

4.3.1 OPEN / IWRS

Patient enrollment will be facilitated using the Oncology Patient Enrollment Network (OPEN). OPEN is a web-based registration system available to users on a 24/7 basis. It is integrated with the CTSU Enterprise System for regulatory and roster data interchange and with the Theradex Interactive Web Response System (IWRS) for retrieval of patient registration/randomization assignment. Patient enrollment data entered by Registrars in OPEN / IWRS will automatically transfer to the NCI's clinical data management system, Medidata Rave.

The OPEN system will provide the site with a printable confirmation of registration and treatment information. Please print this confirmation for your records.

4.3.2 OPEN/IWRS User Requirements

OPEN/IWRS users must meet the following requirements:

- Have a valid CTEP-IAM account (*i.e.*, CTEP username and password).
- To enroll patients or request slot reservations: Be on an ETCTN Corresponding or Participating Organization roster with the role of Registrar. **Registrars must hold a minimum of an AP registration type.**
 - To approve slot reservations or access cohort management: Be identified to Theradex as the "Client Admin" for the studySlot enrollment will be used for the first 10 patients in each arm for the colorectal cancer cohort to allow for the parallel Simon two-stage designs. For the NSCLC cohorts, slot enrollment will be used for the first 20 patient in each arm to allow for an early safety look after 10 patients per arm, and for an interim evaluation of efficacy at 20 patients per arm.
- Have regulatory approval for the conduct of the study at their site.

Prior to accessing OPEN/IWRS, site staff should verify the following:

- All eligibility criteria have been met within the protocol stated timeframes.
- If applicable, all patients have signed an appropriate consent form and HIPAA

authorization form.

4.3.3 Patient Enrollment Instructions

Patients within the NSCLC cohort will be randomly assigned in a 1:1:1 allocation to MEDI4736(durvalumab)/tremelimumab alone
or to
MEDI4736(durvalumab)/tremelimumab with either high- or low-dose radiation.

Patients enrolled to the colorectal cancer cohort will be randomized in a 1:1 allocation to MEDI4736(durvalumab)/tremelimumab with either high- or low-dose radiation.

The randomization schemes will be developed and conducted separately.
Within each cohort, the randomization will be based on the permuted block method.

4.3.5 Digital RT Submission Using Triad

Patients will have their treatment plans submitted to IROC Rhode Island via TRIAD. See section 5.1 Radiation therapy 9) Compliance criteria for details of the data to be submitted.

TRIAD is the American College of Radiology's (ACR) image exchange application. TRIAD provides sites participating in clinical trials a secure method to transmit DICOM, DICOM RT and other objects. TRIAD anonymizes and validates images as they are transferred.

TRIAD Access Requirements

Site radiation therapy staff who will submit data images through TRIAD will need to be registered with the Cancer Therapy Evaluation Program (CTEP) and have a valid and active CTEP Identity and Access Management (IAM) account, **and be registered as an AP, NPIVR or IVR. Please refer to the CTEP Registration Procedures section for instructions on how to request a CTEP-IAM account and complete registration in RCR.**

To submit data via TRIAD, the site user must be on the site's roster and be assigned the 'TRIAD site user' role in RSS.. Users should contact their site's CTSU Administrator or Data Administrator to request assignment of the TRIAD site user role.

TRIAD Installations

When a user applies for a CTEP-IAM account with the proper user role, he/she will need to have the TRIAD application installed on his/her workstation to be able to submit data. TRIAD installation documentation can be found by following this link <https://triadinstall.acr.org/triadclient/>

This process can be done in parallel with obtaining your CTEP-IAM account username and password.

If you have any questions regarding this information, please send an e-mail to the TRIAD Support mailbox at [contact].

4.3.6 Patient Registration for ePRO (Medidata Patient Cloud)

This study includes the use of Medidata Patient Cloud ePRO, (electronic patient-reported outcomes). After the patient is registered to the trial, the CRA (Clinical Research Associate) will complete a second registration to the Patient Cloud ePRO. The CRA will create a unique patient registration code by accessing the Patient Cloud ePRO through iMedidata. Patients (with assistance from CRAs) will need to download the Patient Cloud ePRO app onto their own device and use the unique registration code given by the CRA to create an account. Once completed, the patient will be able to complete the submission of patient reported outcomes electronically.

If sites intend to use a shared institutional device, the CRA can assist the patient with access and registration to the Patient Cloud ePRO app, with the patient completing the electronic data submission independently. Detailed instructions are included in Appendix D. If patients will be using devices supplied by the institution, CRAs will need to help the patient log into the device registration to the Patient Cloud are included in Appendix D.

4.4 General Guidelines

Following registration, patients should begin protocol treatment within 28 days. Issues that would cause treatment delays should be discussed with the Principal Investigator. If a patient does not receive protocol therapy following registration, the patient's registration on the study may be canceled. The Study Coordinator should be notified of cancellations as soon as possible.

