13.2 Endpoint Definitions

13.2.1 Primary Endpoint

At each restaging, patients will be classified as achieving one of the following according to RECIST criteria: complete response (CR), partial response (PR), stable disease (SD), progressive disease (PD), or unevaluable for response, which includes early death from malignancy, toxicity, or other causes in addition to missing or unknown response. Best overall response will be calculated as the best response recorded from the date of randomization for each patient, taking as reference for progressive disease the smallest measurements recorded since the start of treatment. Objective response rate (ORR) is defined as the proportion of patients within a treatment arm who have a best response of either CR or PR. The denominator used to calculate ORR within a treatment will be the number of patients randomized to the respective treatment arm. All randomized patients will be used in randomized comparisons across arms. For single arm evaluation of response, all patients who started treatment will be considered evaluable.

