13.2.2 Secondary Endpoints

Progression-free survival (PFS): Time from date of randomization until objective disease progression (per RECIST) or death, whichever occurs first. For patients without progression, follow-up will be censored at the date of last adequate restaging, unless death occurs within 12 weeks following the date last known progression-free, in which case the death will be counted as a PFS event.

Overall survival (OS): Time from randomization to death from any cause. For patients lost to follow-up or who have no documentation of death at the time of final analysis, follow-up will be censored at the date of last assessment of vital status.

Objective Response per Immune-Related Response Criteria (irORR): The proportion of patients within a treatment arm who have a best response of irCR or irPR according to Immune-Related Response Criteria. The denominator used to calculate irORR within each treatment will be the

number of patients randomized to the respective treatment arm.

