13.3 Randomization

13.3.1 NSCLC

Patients enrolled in the NSCLC cohort will be randomly assigned in equal proportions to therapy with MEDI4736(durvalumab)/tremelimumab alone, MEDI4736(durvalumab)/tremelimumab with low-dose RT, or MEDI4736(durvalumab)/tremelimumab with high-dose RT. Forty patients will be assigned to each of the three therapies (120 in total).

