13.4 Sample Size/Accrual

13.4.1 Sample Size

NSCLC: Best overall response rate is the endpoint on which the sample size for cohort 1 is based. We estimate an overall response rate of approximately 5% for the combination of MEDI4736 and tremelimumab alone based on a comparison of preliminary response rates from patients treated with dual checkpoint blockade of PD-1 and CTLA-4 (Hellman et al. ASCO 2016) as compared with PD-1 inhibitor monotherapy [6]. Two, pair-wise comparisons of therapy with high- or low-dose radiation against the control of MEDI4736(durvalumab)/tremelimumab alone will be conducted. Since a positive outcome for each comparison in this trial is the superiority of MEDI4736(durvalumab)/tremelimumab with high- or low-dose RT compared with MEDI4736(durvalumab)/tremelimumab alone, we propose one-sided chi-squared tests for the null hypothesis of equality of the response rates with a 10% type-I error for each comparison. To assess for early evidence of futility or superiority of MEDI4736(durvalumab)/tremelimumab plus RT, each pairwise comparison will be based on a group sequential design with O'Brien-Fleming stopping boundaries for superiority and Gamma family boundaries ($\gamma=1$) for futility.

When the total sample size in each comparison is 80 patients (40 per arm), a chi-squared test will have 81% power to detect a difference between a 5% response rate and 22% response rate. Interim and final analyses will be conducted after 40 and 80 patients have objective response classifications (corresponding to 50% and 100% of the total information). The critical values $z_{SEP}^{[1]}$ of the test statistic for superiority of MEDI4736(durvalumab)/tremelimumab with RT in each comparison for the interim and final analyses would be 2.054 and 1.317, corresponding to nominal significance $z_{SEP}^{[1]}$ levels of 0.02 and 0.094, respectively. If the p-value at the interim analysis is greater than 0.463 (i.e., the test statistic is less than 0.0922), there will be insufficient evidence to reject $z_{SEP}^{[1]}$ the null hypothesis and the trial for that comparison (and enrollment to the respective RT arm)

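### Section 4.4 allows the registration of a randomised patient who never starts therapy to be cancelled, and no section assures OS and PFS follow-up for such patients, mainly in the NSCLC cohort

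*Combined protocol and SAP*

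**What the plan says.** **Registration and randomisation are one step.** Section 4.3.1 links OPEN to the web response system "for retrieval of patient registration/randomization assignment" and adds: "The OPEN system will provide the site with a printable confirmation of registration and treatment information". The arms are no RT, 24 Gy in three fractions, or repeated low-dose RT. No blinding is described, so I take the trial to be open-label by inference.

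**Start and cancellation.** Section 4.4: "Following registration, patients should begin protocol treatment within 28 days". Then: "If a patient does not receive protocol therapy following registration, the patient's registration on the study may be canceled". Delays are to be discussed with the Principal Investigator, and the Study Coordinator is to be told of cancellations. The section gives no criteria, names no decision-maker, and does not separate cancellation before arm release from cancellation after it.

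**Follow-up.** Section 5.5 gives at least 12 weeks after removal from study treatment and at least a year from treatment initiation. Section 5.6 keeps patients on follow-up once study treatment is terminated.

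**Analysis.** Section 13.2.1 sets the ORR denominator as the number randomised to the arm: "All randomized patients will be used in randomized comparisons across arms". Early death and missing response are unevaluable, and only CR or PR count as response. Section 13.2.2 defines OS as "Time from randomization to death from any cause", with the same origin for PFS, and 13.8.2 compares both by log-rank test in cohort 1. Section 13.9.2 leaves room to omit patients given no study drug from the main response analysis. For single-arm response evaluation, 13.2.1 uses patients who started treatment.

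**The concern.** Cancelling a registration after the arm is known is a discretionary removal after randomisation. If the reason for not starting is related to the arm, for example a patient who declines once told there will be no radiation, the remaining groups are no longer those that randomisation formed.

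The part most exposed is survival. Response can be scored as failure from the assignment alone. OS and PFS need dates, and nothing in the plan obliges a site to collect them for someone who never started. Correcting the analysis text in section 13 would not recover dates that were never collected.

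**Working it through.** **1. The route through the text, for a patient who is randomised and then not treated.**

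| Question | Section | Answer |
|---|---|---|
| Does the site know the arm? | 4.3.1 | Yes, at registration |
| May the registration be cancelled? | 4.4 | Yes, at discretion |
| Does 4.4 end data collection? | 4.4 | Not stated |
| Does any follow-up clock start? | 5.5, 5.6 | No; each clock needs treatment to have started or ended |
| Is the patient in the ORR denominator? | 13.2.1 | Yes, as a non-responder |
| | 13.9.2 | May be omitted |
| Is there an OS and PFS time? | 13.2.2 | Yes, from randomisation |
| | 11.1.6 | PFS has no origin, because it starts with treatment |

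Under the censoring rules of 13.2.2, a patient with no contact after randomisation is censored at or near time zero. Such a patient leaves the risk set before almost any event, so in a log-rank test the effect is close to exclusion.

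**2. The plan's own figure.** Section 13.4.1 states: "we propose one-sided chi-squared tests for the null hypothesis of equality of the response rates with a 10% type-I error for each comparison". It gives 81% power for 5% vs 22% with 40 per arm, boundaries z = 2.054 (interim) and 1.317 (final), and futility below 0.0922. A two-stage calculation with these boundaries and binding futility gives 80.3% (pooled variance) to 82.2% (unpooled), so 81% reproduces. It assumes 40 analysed per arm, and no allowance for untreated patients is stated.

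**3. Equal loss in both arms.** The untreated rate is not in the documents, so k = 1 to 6 of 40 per arm is assumed. The fixed-sample power is

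power = Φ{[δ − z(1−α)·√(2p̄(1−p̄)/n)] / √(p₁(1−p₁)/n + p₂(1−p₂)/n)}, with α = 0.094.

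At n = 40, δ = 0.17 and p̄ = 0.135 this gives 82.6%. Keeping the k patients as non-responders multiplies both rates by (40−k)/40. Removing them sets n = 40−k.

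| k per arm | Kept as non-responders | Removed |
|---|---|---|
| 1 | 81.7% | 81.8% |
| 2 | 80.8% | 81.0% |
| 4 | 78.8% | 79.4% |
| 6 | 76.7% | 77.6% |

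The two policies differ by at most 0.9 points (77.6 − 76.7).

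**4. Unequal loss.** The statistic is z = (p_RT − p_C)/√[p̄(1−p̄)(1/n_RT + 1/n_C)], against 1.317 at the final analysis. For 5/40 vs 2/40, p̄ = 7/80 = 0.0875 and z = 0.075/√(0.0875 × 0.9125 × 0.05) = 0.075/0.0632 = 1.187.

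| RT | Control | Removed | z | Crosses 1.317? |
|---|---|---|---|---|
| 5/40 | 2/40 | none | 1.187 | no |
| 5/37 | 2/40 | 3 RT | 1.298 | no |
| 5/36 | 2/40 | 4 RT | 1.338 | yes |
| 5/36 | 2/39 | 4 RT, 1 control | 1.303 | no |
| 5/36 | 2/36 | 4 each | 1.193 | no |
| 5/40 | 2/36 | 4 control | 1.045 | no |
| 7/40 | 3/40 | none | 1.352 | yes |
| 7/40 | 3/36 | 4 control | 1.180 | no |

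Lopsided loss can change the call in either direction. Balanced loss changes almost nothing. The reduced denominators arise only if cancelled patients are treated as not randomised or the 13.9.2 exception is used.

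**The case against.** The strongest reply is that 13.2.1 already settles the primary endpoint. A never-treated patient needs only a recorded assignment to count as a non-responder, and 4.3.1 says enrolment data transfer automatically to Rave. A reader might infer from 4.4 that the all-randomised denominator cannot be produced. The documents do not support that. What remains open is whether a cancelled registration still counts as randomised, and the contrary wording in 13.9.2.

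Second, 4.4 is permissive and does not say that records or follow-up stop. A reader might infer that a cancelled patient loses all scans and vital status. That goes beyond the text: follow-up is not forbidden, but neither is it required anywhere.

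Third, the significance flip is a selected case. It needs four RT patients lost and no controls, and a single control loss undoes it. The refusal most easily imagined, by patients assigned no radiation, lowers z. This objection stands, and the tables are illustrations only.

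Fourth, a reader might use the roughly six-month median survival in 2.1 to argue that many patients die before starting. That figure describes further chemotherapy after progression, whereas this trial requires ECOG 0–1 and applies life-expectancy criteria. All arms begin with the same infusions and RT follows in week 2, so deaths before the first dose should be similar across arms. Arm-related refusal is the more plausible source of bias.

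**Conclusion.** The point holds as a gap in trial conduct, chiefly for OS and PFS in cohort 1. Following 4.4, 5.5 and 5.6 as written, a randomised patient who never starts can leave the study with the arm known and with no required vital status or progression data, although 13.2.2 and 13.8.2 need both from randomisation. Cohort 1 ORR is protected on a strict reading of 13.2.1; the protection depends on cancelled patients still counting as randomised and on not using the 13.9.2 exception. Cohort 2's single-arm response analysis already uses only treated patients and is unaffected.

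The size cannot be stated, because no untreated rate is given. On the assumed counts, balanced loss costs little, while a four-to-zero imbalance can move the final z across 1.317 either way. The conclusion rests on two inferences: that the trial is open-label, and that a cancelled patient may not be followed because no section requires it. No figure in the plan is shown to be wrong. This is an inexpensive correction worth making.

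**What to change.** In 4.4, state that a registration may be cancelled only before the arm assignment is released. After release, a patient who does not start stays on study as randomised, not treated, with arm, reason and vital status recorded. The patient counts as a non-responder in the cohort 1 randomised comparisons and, unless consent is withdrawn, is followed for survival and, where scanned, for progression.

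Align the related text: give 5.5 and 5.6 a follow-up rule for never-treated patients that runs from randomisation, make 13.9.2 agree with 13.2.1, and bring the PFS origin in 11.1.6 into line with 13.2.2. Report never-treated patients by arm with reasons. Leave the cohort 2 single-arm response rule as it is.

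The cost is a few sentences, one disposition field and vital-status contact for what should be a small number of patients. The reported ORR may be slightly lower than with untreated patients left out.
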